The European society of cardiology guidelines recognised a number of different HRV measures. Time domain measures are the simplest method of analysis of HRV. In a continuous ECG recording, the time between adjacent R wave peaks of QRS complexes is detected. This time interval is termed the N-N interval. Simple statistical tests are then applied to the N-N interval to determine the HRV, these include the standard deviation of the N-N interval (SDNN), square root of the mean squared differences of the N-N interval (RMSSD), the number of interval differences of successive N-N intervals greater than 50ms (NN50), and the proportion derived by dividing NN50 by the total number of NN intervals (pNN50).² Frequency domain measures

make use of power spectral density analysis and fast fourier transform analysis to provide information on how power distributes as a function of frequency.² This technique splits the ECG waveform into small subunits/epochs of time depending upon whether high frequency, low frequency or very low frequency measures are required (see below). The epochs of ECG waveform recording is then transformed from a temporal signal into a spectral representation whereby ECG signal is expressed as the sum of multiple sinusoidal waves of a given amplitude and frequency. These amplitudes are then plotted to give the power spectrum by plotting power versus frequency. Spectral components include frequencies measured HF domain(0.15-0.4Hz) thought to represent the parasympathetic input, LF domain (0.04-0.15Hz) thought to represent the sympathetic nervous system and the parasympathetic nervous system, VLF domain (<0.04Hz) and the ultra-low frequency (ULF) domains (<0.003Hz).²⁷ Measurement of the frequencies can be made in absolute values, but are often recorded as normalised units which represents the relative value of each power component in proportion to the total power minus the VLF component.⁸² Non-linear methods include measures such as the Poincare plot.² In the Poincare plot an individual's N-N interval is plotted against time and standard deviation used to interpret changes.⁹ The Poincare plot is described by two descriptors, SD1 is the fast beat-to-beat variability in the R-R intervals whilst SD2 describes the longer variability.^{9,2} SD1 reflects mainly the parasympathetic component of the autonomic nervous system, whilst SD2 reflects the parasympathetic and sympathetic components.⁹

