4.3 Schedule of study procedure

With informed consent, the following routinely recorded clinical and laboratory data will be collected:

- Baseline demographics and comorbidities
- Administration of beta blockers or anti-arrhythmics
- Administration of sedative agents (general anaesthetics/opioids/benzodiazepines)
- Reasons for admission to ICU
- Daily biochemistry and haematology results
- Severity of illness scores, including APACHE II and daily SOFA scores
- Daily CAM ICU scores / delirium
- Daily cardiac rhythm as per nursing entry or clinical diagnosis
- Daily clinical parameters, including medications (vasopressors/ionotropes/steroids/muscle relaxants) and organ support
- Daily AKI stage, including treatment with RRT

After obtaining informed consent, continuous ECG data will be recorded using the two different devices. ECG data will then be processed to derive HRV using the methodology described by the European Society of Cardiology Taskforce guidelines.² Processing of ECG data entails checking

for and removal of extrasystole and ectopic beats with interpolation of QRS complexes as described elsewhere.² Continuous 24 hour ECG recording will then be divided into 5 minute epochs for which short term HRV values will be calculated. HRV will be calculated in the time domain, frequency domain and non-linear domains for each 5 minute epoch. Entire 24 hour ECG recordings will be used for long term HRV measures in the time domain, frequency domain and non-linear domains as described the Taskforce guidelines.² HRV data will then be analysed according to that described in the statistical methodology and analysis section. HRV data will be calculated by the Medical Engineering and Clinical Physics department at the Royal Liverpool and Broadgreen University Hospital. They will be blinded to any patient identifiable or clinical information.

Daily data will be collected until day 5 in ICU, day of discharge from ICU or day of death (depending on what occurs first). In addition, we will record ICU and hospital length of stay, ICU and hospital mortality and occurrence of arrhythmias during ICU stay, after 30 days, and after 90 days following enrollment. Data will be collected by accessing routinely available results in the patients' medical records, and if necessary, by contacting the patient's General Practitioner (GP).

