Appendix 1: Analysis of HRV variables

Parameter	Units	Description	Normal range
SDNN	ms	Standard deviation of the NN intervals	101.19
SDANN	ms	Standard deviation of average NN intervals	41.47
pNN50	%	Percentage of successive RR intervals that differ by more than 50ms	18.80
RMSSD	ms	Root mean square of successive RR interval differences	0.08
LF power	ms ²	Absolute power of the low frequency band (0.04 – 0.15Hz)	2534.91
HF power	ms ²	Absolute power of the high frequency band (0.15 – 0.4Hz)	2592.32
VLF power	ms ²	Absolute power of the very low frequency band (0.033 – 0.04Hz)	8307.38
LF/HF ratio	%	Ration of LF to HF power	128.78
SD1	ms	Poincre plot standard deviation perpendicular to the line of identity	57.01
SD2	ms	Poincre plot standard deviation along the line of identity	134.13
SD1/SD2 ratio	%	Ratio of SD1 to SD2	2.49

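### Appendix 1 sets the VLF band at 0.033–0.04 Hz, which contradicts section 1 and, if coded as written, would measure about 19% of the implied band width

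*Protocol*

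**What the plan says.** Section 1 (Introduction) describes the spectral bands. For the two lowest it gives "VLF domain (<0.04Hz) and the ultra-low frequency (ULF) domains (<0.003Hz". It states no explicit lower limit for VLF, but the ULF ceiling implies one of about 0.003 Hz.

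Appendix 1, the table of HRV variables for analysis, gives VLF as "Absolute power of the very low frequency band (0.033 – 0.04Hz". It has no ULF row. Its other two bands, "Absolute power of the low frequency band (0.04 – 0.15Hz" for LF and "Absolute power of the high frequency band (0.15 – 0.4Hz" for HF, agree exactly with section 1. Only VLF differs.

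Three other parts of the protocol bear on the consequence:

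- Section 4.3 sets the short-term analysis unit: "Continuous 24 hour ECG recording will then be divided into 5 minute epochs".
- Section 2.3 sends Holter recordings through the Holter software and Isansys RR intervals through an in-house Matlab program. It then plans a Bland-Altman comparison for each HRV measure.
- Sections 2.3 and 4.3 say that HRV is derived according to the Taskforce guidelines. Neither sets band limits of its own.

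**The concern.** A band limit is part of the definition of a spectral power: change the limit and the quantity changes. Here the protocol gives two incompatible definitions of VLF, and the narrower one stands in the table that a programmer would most naturally consult.

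What is at stake is the device comparison. Frequency-domain agreement between Isansys and Holter is a secondary outcome, and section 2.3 makes agreement the basis for calling the devices interchangeable. Because each device has its own software, a band limit entered in one and not the other would appear in the Bland-Altman plot as bias between devices, although neither sensor was at fault. A further secondary objective is to define changes in data capture and analysis for a larger trial, so an uncorrected limit could be carried forward.

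**Working it through.** **Inputs**

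- Appendix 1: VLF from 0.033 to 0.04 Hz.
- Section 1: VLF upper limit 0.04 Hz; ULF ceiling 0.003 Hz, taken as the VLF lower limit.
- Section 4.3: 5-minute (300 s) epochs.
- Assumption, not in the protocol: the shape of the spectrum within VLF. Flat, 1/f and 1/f² are shown as a range.

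**Step 1: can section 1 yield the Appendix band?** Three readings of the lower limit were tried.

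| Lower limit taken | Implied width (Hz) | Appendix width / implied width |
|---|---|---|
| 0.003 Hz (ULF ceiling) | 0.037 | 0.007/0.037 = 18.9% |
| 0.0033 Hz (1/300 s, the resolution of a 5-minute epoch) | 0.0367 | 0.007/0.0367 = 19.1% |
| 0 Hz (section 1 read literally) | 0.040 | 0.007/0.040 = 17.5% |

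None gives 0.033 Hz. The conflict does not depend on how section 1 is read.

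**Step 2: share of 0.003–0.04 Hz power that lies in 0.033–0.04 Hz**

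- Flat: 0.007/0.037 = 18.9%.
- 1/f: ln(0.04/0.033) / ln(0.04/0.003) = 0.1924/2.5903 = 7.4%.
- 1/f²: (1/0.033 − 1/0.04) / (1/0.003 − 1/0.04) = 5.303/308.33 = 1.7%.

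So 81% to 98% of the power in the implied band would be left out.

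**Step 3: what that does to the comparison.** Suppose both devices delivered the same RR series, the Matlab route used 0.033–0.04 Hz and the Holter route 0.003–0.04 Hz. Holter VLF power would then exceed Matlab VLF power by a factor of 1/0.189 = 5.3 (flat), 1/0.0743 = 13.5 (1/f) or 1/0.0172 = 58 (1/f²), from settings alone.

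**Step 4: frequency resolution.** A 300 s epoch resolves 1/300 = 0.0033 Hz. The Appendix band then spans 0.007 × 300 = 2.1 frequency bins, against 0.037 × 300 = 11.1 for the implied band.

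**Step 5: what is untouched.** LF (0.04–0.15 Hz), HF (0.15–0.4 Hz) and therefore LF/HF use limits that agree in both places. The time-domain and Poincaré measures use no band limits. The primary outcome counts interpretable epochs and does not involve VLF.

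**The case against.** The strongest reply is that this is a slipped decimal with no demonstrated effect. The body of the protocol never says that the Matlab program takes its limits from Appendix 1. The program is described as already developed, and derivation is tied to the Taskforce guidelines. The Holter software's bands are not stated either. The two routes may also differ at low frequencies for other reasons: the Ornstein-Uhlenbeck step is described in the title of its cited source as detrending and low-pass filtering. All of this stands, and it makes the harm conditional. It does not remove the contradiction. A protocol that defers to a guideline while printing a conflicting limit in its own variable table gives the programmer two instructions.

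Two stronger readings are tempting, and neither is supported.

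- **Normalised units.** A reader might infer that LF and HF in normalised units would be wrong as well, since section 1 defines them by "relative value of each power component in proportion to the total power minus the VLF component". But section 1 mentions such units only as background ("Measurement of the frequencies can be made in absolute values, but are often recorded as normalised units"), and Appendix 1 lists absolute powers and LF/HF. Total power is not defined. If it is the sum of the computed bands, then (VLF + LF + HF) − VLF = LF + HF and the VLF limit cancels. An error arises only if total power spans the full spectrum while VLF uses the narrow band.
- **The listed VLF value.** A reader might argue that the Appendix's 8307.38 ms² is too large for so narrow a band and so proves a misprint. That column cannot carry the argument. It lists RMSSD as 0.08 ms beside SD1 of 57.01 ms, although RMSSD is about √2 × SD1 = 80.6 ms. It lists LF/HF as 128.78% beside powers whose ratio is 2534.91/2592.32 = 97.8%.

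**Conclusion.** The point holds as an internal contradiction in an analysis definition. Appendix 1 and section 1 give VLF lower limits that differ about tenfold, and under Appendix 1 the range 0.003–0.033 Hz falls in no band. This is certain from the text, apart from the exact figure of 0.003 Hz, which is inferred from the ULF ceiling.

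The consequence is conditional. If the in-house program follows Appendix 1, VLF power covers about 19% of the implied width (17.5–19.1% across readings) and about 2–19% of its power (1/f² to flat, an assumed range). If the Holter software uses the wider band, the device comparison for VLF is distorted several-fold or more. If both routes used the Appendix limit, there would be no artefact from this source, but both would report something other than the VLF that section 1 describes.

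The reach is one measure within one secondary comparison of a feasibility study. It should be corrected before analysis because it is cheap to correct. It does not threaten the primary outcome.

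**What to change.** - Correct the VLF lower limit in Appendix 1 to agree with section 1, at about 0.003 Hz (the ULF ceiling).
- State the same explicit lower limit in section 1, which now only implies it.
- Check the settings of the Matlab program and of the Holter software, and confirm in writing that both use that limit. If the Holter limit is fixed by the vendor and differs, set the Matlab limit to match for the comparison, or report VLF as not comparable between devices.
- Only if normalised units are to be reported, define total power and use the same VLF limit in it.

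The cost is one corrected line in Appendix 1, a few words in section 1 and one parameter check in each route. No patients, recordings or extra data are needed.

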Appendix 2 – Information with regards to Safety Reporting in Non-CTIMP Research

	Who	When	How	To Whom
SAE	Chief Investigator	Report to sponsor within 24 hours of learning of the event Report to the MREC within 15 days of learning of the event	SAE report form for non-CTIMPs, available from NRES website.	Sponsor and MREC
Urgent Safety Measures	Chief Investigator	Contact the sponsor and MREC immediately Within 3 days	By phone Substantial amendment form giving notice in writing setting out the reasons for the urgent safety measures and the plan for future action.	Main REC and sponsor Main REC with a copy also sent to the sponsor. The MREC will acknowledge this within 30 days of receipt.
Progress Reports	Chief Investigator	Annually (starting 12 months after the date of favourable opinion)	Annual progress report form (non-CTIMPs) available from the NRES website	Main REC
Declaration of the conclusion or early termination of the study	Chief Investigator	Within 90 days (conclusion) Within 15 days (early termination) The end of study should be defined in the protocol	End of study declaration form available from the NRES website	Main REC with a copy to be sent to the sponsor
Summary of final Report	Chief Investigator	Within one year of conclusion of the research	No standard format However, the following Information should be included: Where the study has met	Main REC with a copy to be sent to the sponsor

			its objectives, the main findings and arrangements for publication or dissemination including feedback to participants	
--	--	--	--	--

12. References

2. Guidelines Heart rate variability Standards of measurement, physiological interpretation, and clinical use. *Eur. Heart J.* **17**, 354–381 (1996).
3. Karmali, S. N., Sciusco, A., May, S. M. & Ackland, G. L. Heart rate variability in critical care medicine: a systematic review. *Intensive Care Med. Exp.* **5**, 33 (2017).
4. McCraty, R. & Shaffer, F. Heart Rate Variability: New Perspectives on Physiological Mechanisms, Assessment of Self-regulatory Capacity, and Health Risk. *Glob. Adv. Heal. Med.* **4**, 46–61 (2015).
